1. INTRODUCTION

This statistical analysis plan (SAP) specifies the statistical methods to be implemented for the analysis of data collected from the SPECTRUM 6 study within the scope of Santen's Protocol 011712IN, "A Randomized, Double-Masked, Parallel-Group, Multicenter Study Assessing the Safety and Efficacy of DE-117 Ophthalmic Solution 0.002% Once Daily and Twice Daily in Subjects with Primary Open-Angle Glaucoma or Ocular Hypertension - SPECTRUM 6 Study". It applies to the study protocol dated 13 Nov 2018 and provides detailed instructions as to how each analysis will be performed.

Results obtained from the analyses specified in the final approved version of the SAP will become the basis of the clinical study report (CSR) for this study. Any deviations from the final approved version of the SAP must be substantiated by sound statistical reasoning and documented in the CSR.

2. OBJECTIVE(S) AND ENDPOINTS

Table 1: Study Objectives and Endpoints

| Study Objectives | Corresponding Study Endpoints |
|---|---|
| 
Primary Objective:
 
To determine whether DE-117 Ophthalmic Solution 0.002% given BID is superior to QD in reducing the intraocular pressure (IOP) after 6 weeks of treatment in subjects with POAG or OHT.
 | 
Primary Efficacy Endpoint:
 
The primary efficacy endpoint is the IOP in the study eye measured at the specified time points: 08:00, 12:00 and 16:00 at Week 2 (Visit 3) and Week 6 (Visit 4).
 
Secondary Efficacy Endpoints:
 
 • Mean diurnal IOP in the study eye at Week 6 (Visit 4) • Absolute change and percent change from baseline in IOP • Absolute change and percent change from baseline in mean diurnal IOP • Having a mean diurnal IOP reduction $\geq 20\%$, $\geq 25\%$, or $\geq 30\%$ from Baseline (Visit 2) at each post-baseline visit • Having a mean diurnal IOP ≤ 18 mmHg at each post-baseline visit |

Table 1: Study Objectives and Endpoints (Continued)

| Study Objectives | Corresponding Study Endpoints |
|--|--|
| 
Safety Objective: To determine the safety of DE-117 ophthalmic solution 0.002% given BID as compared to QD in subjects with POAG or OHT.
 | 
Safety Endpoints: Safety will be evaluated by the following parameters:
 
 • Incidence of ocular and systemic AEs • Best-corrected visual acuity (BCVA) • Slit-lamp biomicroscopy findings: anterior chamber cells, anterior chamber flare, lid hyperemia, lid edema, conjunctival hyperemia, conjunctival chemosis, corneal edema, corneal staining, keratin precipitates, abnormal lens findings, anterior synechiae of iris, posterior synechiae of iris • Ophthalmoscopy |

3. STUDY DESIGN

[figure not shown]
3.1. General Study Design

This is a randomized, double-masked, parallel-group, multi-center study. Subjects diagnosed with POAG or OHT who meet eligibility criteria at Visit 1 (Screening) will wash out their current topical IOP lowering medication(s), if any. After completing the required washout period, subjects will return for Visit 2 (Baseline, Day 1). Subjects who meet all eligibility criteria at Visit 2 will be randomized to receive study medication for up to 6 weeks.

Approximately 100 subjects with POAG or OHT will be randomized in a 1:1 ratio to either:

- DE-117 ophthalmic solution 0.002% QD (20:00) and Vehicle QD (08:00), or
- DE-117 ophthalmic solution 0.002% BID (20:00 & 08:00)

As shown in the Study Schema ([Figure 1](#)), this study will consist of a screening period of up to 35 days including a washout period of up to 28 days (+ 7 days window), and a 6-week double-masked treatment period.

Figure 1: Study Schema

At Screening (Visit 1), subjects who provide written informed consent and meet all eligibility criteria are required to wash out any IOP-lowering medication(s) they are using, or wait at least one day if they have not used an IOP-lowering medication for the last 28 days, before returning for further eligibility assessments at baseline (Visit 2; Day 1). Subjects who meet all eligibility criteria at baseline will be randomized in a 1:1 ratio to receive either DE-117 0.002% QD in the evening and vehicle QD in the morning or DE-117 0.002% BID for 6 weeks with scheduled Visits 2, 3 and 4 (Baseline, Week 2 and Week 6). Post-baseline safety and efficacy measures will be collected at scheduled visits and Study Exit/Early Termination (ET) according to the Assessment Schedule (Table 2).

3.2. Randomization and Masking

A permuted-block randomization will be employed to randomize eligible subjects in a 1:1 ratio to either DE-117 QD/Vehicle QD arm or DE-117 BID arm. The randomization schedule will be generated and implemented using central randomization via Interactive Response Technology (Medidata Balance/RTSM).

Treatment assignments will be masked to Santen, study subjects, and Clinical Investigator. The appearance of the bottles of DE-117 ophthalmic solution 0.002% and the vehicle will be identical. All subjects will receive bottles labeled "morning" for the morning dose and bottles labeled "evening" for the evening dose. Each eligible subject will be assigned to receive a numbered study medication kit as assigned by central randomization via Interactive Response Technology at Visit 2 (Baseline). In case of a medical emergency, the Principal Investigator may reveal the treatment information by unmasking through Medidata Balance/RTSM to know which treatment the subject has received.

3.3. Sample Size Planning

The sample size calculation does not consider multiplicity from multiple time points. Assuming a two-sided type I error rate of 5% and a standard deviation of 3.5 mmHg, approximately 50 subjects per treatment arm (100 in total) will have about 80% power to detect a 2.0 mmHg between-treatment difference.

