9.1. Statistical Hypotheses

The primary efficacy endpoint is the IOP at each scheduled time point (08:00, 12:00 and 16:00) in the study eye at Week 2 and 6 (Visit 3 and 4). The comparison between DE-117 BID arm and QD arm will be performed with the following hypotheses:

$$H_{0i}: \mu_{Bi} = \mu_{Qi}$$

versus

$$H_{1i}: \mu_{Bi} \neq \mu_{Qi}$$

where μ_B and μ_Q denote the mean values of the primary endpoint in DE-117 BID arm and QD arm at $i = 1, 2, \dots, 6$ timepoints, with $i = 1, 2, 3$ represent 08:00, 12:00 and 16:00 at Week 2 and $i = 4, 5, 6$ represent 08:00, 12:00 and 16:00 at Week 6, respectively.

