9.2. Sample Size Determination

The sample size calculation does not take into account of multiplicity from multiple time points. Assuming a two-sided type I error rate of 5% and a standard deviation of 3.5 mmHg, 50 patients per treatment arm (100 in total) will have 80% power to detect a 2.0 mmHg between-treatment difference.

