9.3.6.1. Analysis of Primary Endpoint

The primary efficacy endpoint is IOP in the study eye at each specified timepoint (08:00, 12:00 and 16:00) at Week 2 (Visit 3) and Week 6 (Visit 4). For the primary analysis, a mixed-effect model for repeated measures (MMRM) will be carried out and least squares mean of the endpoint will be reported. The model will include treatment, visit, and treatment-by-visit interaction as fixed effects, baseline IOP as a covariate, and subject as a random effect.

Treatment differences between the DE-117 BID arm and QD arm will be reported for each time point along with p-values and 95% confidence intervals.

Analysis of covariance (ANCOVA) with missing data imputed by an LOCF approach will be used as sensitivity analyses.

In addition, plots of IOP measures versus analysis time/analysis visit will be provided.

9.3.6.2. Analysis of Secondary Efficacy Endpoints:

- Mean diurnal IOP in the study eye at Week 6 (Visit 4)
- Absolute change and percent change from baseline in IOP
- Absolute change and percent change from baseline in mean diurnal IOP
- Having a mean diurnal IOP reduction $\geq 20\%$, $\geq 25\%$, or $\geq 30\%$ from Baseline (Visit 2) at each post-baseline visit
- Having a mean diurnal IOP ≤ 18 mmHg at each post-baseline visit

Continuous secondary efficacy endpoints will be analyzed by a mixed-effects model for repeated measures (MMRM) using observed cases or analysis of covariance (ANCOVA) with missing data imputed by an LOCF approach. Binary secondary efficacy endpoints will be analyzed using Pearson's Chi-square test.

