6.4. Multiple Comparisons / Multiplicity

No multiplicity adjustment will be applied in this study. Treatment differences in IOP between DE-117 QD arm and DE-117 BID arm for each timepoint will be considered statistically significant if the *p*-value of the corresponding treatment comparison is smaller than 0.05. Superiority of DE-117 BID to DE-117 QD is achieved if the treatment differences are significantly greater than 0 at all six time points.

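### The 80% power in SAP 3.3 and Protocol 9.2 is for one time point; SAP 6.4 requires all six, and the power of that rule is not stated and is lower under the same inputs

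*SAP*

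**What the plan says.** SAP 3.3 states that "approximately 50 subjects per treatment arm (100 in total) will have about 80% power to detect a 2.0 mmHg between-treatment difference". The inputs are a two-sided type I error of 5% and an SD of 3.5 mmHg. No time point is named for the 2.0 mmHg. The section also says: "The sample size calculation does not consider multiplicity from multiple time points". Protocol 9.2 has the same inputs and result ("50 patients per treatment arm (100 in total) will have 80% power to detect a 2.0 mmHg between-treatment difference") and the same caveat ("The sample size calculation does not take into account of multiplicity from multiple time points").

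SAP 6.4 sets two rules. The first is per time point: differences between "DE-117 QD arm and DE-117 BID arm for each timepoint will be considered statistically significant" when the p-value is below 0.05, with no multiplicity adjustment. The second decides the trial: "Superiority of DE-117 BID to DE-117 QD is achieved if the treatment differences are significantly greater than 0 at all six time points". The six are 08:00, 12:00 and 16:00 at Weeks 2 and 6.

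The Protocol does not contain the second rule. Section 9.1 introduces six pairs of hypotheses ("The comparison between DE-117 BID arm and QD arm will be performed with the following hypotheses"), and section 9.3.6.1 only reports them: "Treatment differences between the DE-117 BID arm and QD arm will be reported for each time point along with p-values and 95% confidence intervals".

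The primary model in SAP 8.1.1 is an MMRM for each clock time with baseline IOP as covariate. Neither document says whether 3.5 mmHg is the SD before or after that adjustment. Neither gives correlations between time points or a loss allowance.

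**The concern.** The primary objective is superiority of BID over QD, and SAP 6.4 decides it by winning six correlated tests together. The chance of that cannot exceed the chance of winning any one of them, and it is lower unless the six results move in perfect step. The only power figure in either document is for one test.

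The caveat about multiplicity does not close the gap. It is usually read as saying that alpha was not split. A rule that requires every test to succeed needs no alpha split; what it costs is power. Neither sample-size section says that success needs all six tests, or that power for that claim is lower. Someone reading only the Protocol could take 80% as the chance of meeting the primary objective.

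What is at stake is planning and the reading of a negative result. If all-six power is well below 80%, failure at one or two time points is weak evidence against a 2.0 mmHg benefit.

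**Working it through.** **1. Reproduce the stated figure.** Inputs from SAP 3.3: difference d = 2.0, SD s = 3.5, n = 50 per arm, two-sided alpha 0.05.

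- Noncentrality: δ = d / (s√(2/n)) = 2.0 / (3.5 × 0.2) = 2.857.
- Critical value: t with 98 df, 1.984.
- Power (noncentral t): 80.8%. The plan's figure is correct for one comparison.

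**2. Bounds for the all-six rule, same inputs.** Assume a true 2.0 mmHg at all six points and no missing data. If the six tests were independent, power would be about 0.808⁶ = 0.28. If they were perfectly correlated it would be 80.8%. With positive correlation it lies between.

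**3. Values between the bounds (3.5 mmHg is the SD of the comparison).** The documents give no correlations, so an equal correlation ρ is assumed and varied. Up to the estimation of the variance,

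P(all six) = ∫ φ(x) · Φ[(δ − c + √ρ·x) / √(1 − ρ)]⁶ dx, with c = 1.98.

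Simulation with estimated variances agrees to within half a point:

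| ρ | Integral | Simulation, 50 per arm | Difference detectable with 80% all-six power |
|---|---|---|---|
| 0.3 | 41.0% | 40.7% | 2.59 mmHg |
| 0.5 | 49.2% | 48.9% | 2.52 mmHg |
| 0.7 | 57.9% | 57.6% | 2.42 mmHg |
| 0.9 | 68.7% | 68.5% | 2.25 mmHg |

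**4. If 3.5 mmHg is a raw SD.** Adjustment for a baseline with correlation b to each post-baseline value shrinks the SD to 3.5√(1 − b²). For b = 0.5 this is 3.5 × 0.866 = 3.03, so δ = 2.0 / (3.03 × 0.2) = 3.30. The adjustment also lowers the correlation left between time points, to (ρ − b²)/(1 − b²). Simulated ANCOVA with one common baseline, 50 per arm:

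| Assumed b | Single-point power | All-six power, raw ρ 0.3 to 0.9 |
|---|---|---|
| 0.3 | 84% | about 44–72% |
| 0.5 | 90% | about 56–81% |
| 0.7 | 98% | about 87–93% (ρ 0.5 to 0.9 only) |

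At b = 0.7, ρ = 0.3 is not a possible correlation matrix: (1 + 5 × 0.3)/6 = 0.417, which is below 0.7² = 0.49.

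**5. If the effect differs by clock time.** At follow-up visits the 08:00 reading precedes the morning dose and the other two follow it (Protocol 8.1.4 and 8.1.5), so a uniform effect is not assured. With SD 3.5 as in step 3 and ρ from 0.3 to 0.9:

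- 1.5 mmHg at 08:00 and 2.0 at the other times: about 25–49%.
- 2.0 mmHg at 08:00 and 2.5 at the other times: about 59–76%.

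**6. Loss.** Early terminations are not replaced (Protocol 7.2.1), and IOP after non-study IOP-lowering therapy is treated as missing (SAP 6.2.1). With 45 analysed per arm (10% loss, an assumption) and SD 3.5 as in step 3, single-point power is 76.5% and all-six power about 33–63%.

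**The case against.** The strongest reply is that the plan is open about the limitation. Both sample-size sections say multiple time points were left out, the 80% fits the per-time-point rule in SAP 6.4, and anyone who reads SAP 3.3 beside 6.4 can see that 80% is not joint power. All of that is true, but a reader is still not told that the deciding rule has lower power, or how much lower.

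A second reply is that every all-six figure rests on inputs the documents do not give. That also stands. The raw-SD range is driven mainly by the assumed baseline correlation, and the simulation uses one baseline where the SAP may use a time-matched one. The 10% loss case is on the harsh side: it removes subjects from all six tests, although the MMRM keeps partial data and early leavers have Visit 4 assessments where possible. The figures therefore show a range and do not estimate this trial's power.

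Three stronger readings might be inferred, and the documents do not support them:

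- **The calculation is wrong or the trial is certainly underpowered.** The 80% reproduces. If 3.5 mmHg is raw and baseline is strongly predictive, all-six power can reach or pass 80%.
- **Type I error is inflated because nothing is adjusted.** Requiring all six tests, each at 0.05, does not inflate the error of the superiority claim.
- **Protocol 9.2 contradicts the Protocol.** The all-six rule is only in the SAP, so the mismatch is between the power statement and SAP 6.4.

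**Conclusion.** The point holds as an incomplete power statement that should be fixed. The 80% belongs to one comparison. The power of the rule that decides the primary objective appears nowhere. Under the calculation's own inputs it is about 41–68% at assumed correlations 0.3–0.9, given a uniform true difference of 2.0 mmHg, equal correlations and 50 analysed per arm with nothing missing. On those terms a real 2.0 mmHg benefit at every time point would miss superiority in roughly 32–59% of trials.

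The size depends on three things the plan leaves open: whether 3.5 mmHg is raw or baseline-adjusted, the correlations (between time points and with baseline), and the effect profile over the day. Loss would lower it further. The gap itself is certain; the numerical shortfall is conditional. A positive result under the all-six rule remains valid.

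**What to change.** In SAP 3.3, and in Protocol 9.2 at the next amendment:

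1. Describe the 80% as power for each single time point with 50 analysed per arm.
2. Say whether 3.5 mmHg is the raw or the baseline-adjusted SD.
3. State the power of the SAP 6.4 all-six rule, or the difference it detects with 80% power, under declared correlations, effect profile and loss. For scale, at time-point correlations 0.3 to 0.9 that difference is about 2.6 to 2.25 mmHg if 3.5 mmHg is the adjusted SD. It is about 2.3 to 2.0 mmHg if 3.5 mmHg is raw with an assumed baseline correlation of 0.5.
4. Cross-refer from the Protocol's sample-size section to the all-six rule.

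This needs no extra subjects and no change to the analysis or decision rule. The SAP change is wording plus a short calculation. The Protocol change needs IRB/IEC approval (Protocol 10.1.2), so it is best carried with another amendment. The downside is a stated power that will probably, though not certainly, look less favourable.

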3.4. Visits and Assessments

There are 4 scheduled visits for each subject. Assessments at each visit and the time/visit window for each post-baseline assessment are specified in the Assessment Schedule ([Table 2](#)). For subjects whose study participation is terminated prior to Week 6 (Visit 4, Day 43 \pm 3), to the extent possible, all assessments scheduled for Visit 4 will be performed at the Early Termination (ET) visit.

Table 2: Assessment Schedule

| | Washout Period | | Double-Masked Treatment Period | | |
|---|------------------------|--|--|--------------------------------|---|
| | Visit 1 (Screening) | Washout Period (up to 4 weeks) Optional Visit 1 ^k | Visit 2 Eligibility/ Baseline (Day 1) | Visit 3 Week 2 (Day 15±2) | Visit 4 Week 6 (Day 43±3) Exit or Early Termination ^l |
| Informed Consent(s) including the consent for pharmacogenomics/ genomics laboratory research study ^a | X | | | | |
| Inclusion/Exclusion Criteria | X | | X | | |
| Demographics and Medical History | X | | | | |
| Concomitant Medications / Therapies | X | X | X | X | X |
| Dosing Compliance | | | | X | X |
| Adverse Events | | X | X | X | X |
| Pregnancy Test ^b | X | | X | | X |
| Refraction ^c | X | | | | |
| BCVA ^c | X | X | X (prior to 8:00 IOP meas.) | X (prior to 8:00 IOP meas.) | X (prior to 8:00 IOP meas.) |
| Biomicroscopy ^d | X | X | X (prior to 8:00 IOP meas.) | X (prior to 8:00 IOP meas.) | X (prior to 8:00 IOP meas.) |
| IOP ^e | X (any time) | X (any time) | 08:00 12:00 16:00 | 08:00 12:00 16:00 | 08:00 12:00 16:00 |
| Pachymetry ^f | X | | | | |
| Instill study eye drop after 08:00 IOP measurement | | | | X (after to 8:00 IOP meas.) | X (after to 8:00 IOP meas.) |
| Gonioscopy ^g | X | | | | |
| Visual Field ^h | X | | | | |
| Ophthalmoscopy ⁱ | X (pupil dilation) | | X (after 16:00 IOP meas.) | | X (after 16:00 IOP meas., pupil dilation) |
| Blood Sampling for Pharmacogenomics/genomics ^j | | | | X | |
| Dispense Study Medication | | | X | | |
| Collect Study Medication | | | | | X |

Table 2: Assessment Schedule (Continued)

| | Washout Period | | Double-Masked Treatment Period | | |
|---|------------------------|--|--|------------------------------|---|
| | Visit 1 (Screening) | Washout Period (up to 4 weeks) Optional Visit 1 ^k | Visit 2 Eligibility/ Baseline (Day 1) | Visit 3 Week 2 (Day 15±2) | Visit 4 Week 6 (Day 43±3) Exit or Early Termination ^l |
| Phone call to remind subjects to take morning and evening dose on the day before each visit | | | | X | X |

^a Informed Consent(s) including the consent for pharmacogenomics/ genomics laboratory research study

Informed consent form (ICF) must be signed and dated before study procedures are performed. Informed consent for the optional pharmacogenomics/genomics laboratory research study may be obtained at any visit prior to study exit.

^b Pregnancy Test

A urine pregnancy test will be conducted for all female subjects of childbearing potential.

^c Refraction and BCVA

Refraction will be performed at the screening visit. If more than 10 letters in BCVA were lost compared to the screening visit, then refraction should be performed again. BCVA examination will be completed before IOP is measured at 08:00 (±60 min).

^d Biomicroscopy

Biomicroscopy examination must be completed before IOP is measured at 08:00. Aqueous flare and cell evaluation will be performed before fluorescein instillation.

^e IOP

IOP measurements will be performed at 08:00, 12:00 and 16:00 (±60 min) at all visits except for Visit 1 and optional Visit 1a (screening and mid-washout).

^f Pachymetry

Pachymetry will be performed after IOP measurement at Visit 1 (Screening).

^g Gonioscopy

If gonioscopy was performed within 3 months (90 days) prior to screening and was documented in the subject's records, no additional screening gonioscopy examination is necessary.

^h Visual Field

If visual field test was performed within 3 months (90 days) prior to screening and was documented in the subject's records, no additional screening visual field test is necessary.

ⁱ Ophthalmoscopy

Ophthalmoscopy will be performed at Visits 1, 2 and 4 (i.e. Screening, Baseline and Week 6) after the very last IOP measurement. Ophthalmoscopy will be performed with pupil dilation at Visit 1 and Visit 4/ Study Exit or Early Termination. Dilation of the pupil will be performed after the very last IOP measurement at Visit 1 and Visit 4/Study Exit or Early Termination.

^j Blood Sampling for Pharmacogenomics/genomics

Blood sampling for the pharmacogenomics/genomics laboratory research study may be performed at any visit after pharmacogenomics/genomics informed consent is obtained, subject is randomized and study drug, DE-117 ophthalmic solution 0.002%, dosing has begun.

^k Optional Visit 1a

An interim safety visit may be performed during the washout period Visit 1a (optional, mid-washout visit), if in the Investigator's opinion a subject's IOP may be of concern. If subjects are treated with a topical CAI during the washout period. Visit 1a (optional, mid-washout visit) is recommended to be performed.

^l Exit or Early Termination

All listed procedures are required for early terminated subjects.

4. DEFINITIONS

4.1. Time-Related Terms

4.1.1. Baseline Visit

The *Baseline visit* is Visit 2 (Day 1) when the subject is randomized.

4.1.2. Treatment Start and End Dates

Treatment start date is the date at which a randomized subject takes the first dose of the study medication.

Treatment end date is the date at which a randomized subject takes the last dose of the study medication. If the date of the last dose is missing, then

- The day before the Visit 4 (Week 6) will be considered the treatment end date for subjects who completed the study, and
- The day before the Exit Visit date will be used for subjects who prematurely discontinued from the study. If the Exit Visit date of a non-completer is not available, then the day before the last available visit date will be considered the treatment end date.

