medications for the last 28 days, including treatment-naive subjects, must have ≥ 1 day between their screening visit and Visit 2 (Baseline).

At Visit 2, baseline IOP will be measured for both eyes at 8:00 (± 60 min), 12:00 (± 60 min) and 16:00 (± 60 min). The study eye will be the eye that qualifies per eligibility criteria at Visit 2. If both eyes meet the eligibility criteria, the eye with the higher diurnal IOP at Visit 2 will be designated as the study eye. If both eyes meet the eligibility criteria and have the same mean diurnal IOP at Visit 2, the right eye will be designated as the study eye. Both eyes should be treated with the study medication for the duration of the study even if only one eye is eligible per IOP inclusion criteria.

Treatment Period (6 weeks):

Approximately 100 eligible subjects will be randomized to either DE-117 0.002% QD in the evening and vehicle QD in the morning or DE-117 0.002% BID in a 1:1 ratio. Subjects will be treated for 6 weeks with scheduled Visits 2, 3 and 4 (Baseline, Week 2 and Week 6).

At Visit 2 (Baseline), subjects will be instructed to instill their first dose of study medication (study eye drops) as per their assigned/randomized study treatment at 20:00 (± 60 minutes) that same evening. The next day, subjects will subsequently dose their assigned study medication at 08:00 (± 60 minutes) and 20:00 (± 60 minutes). At each scheduled follow-up visit, subjects will instill their morning dose of study medication/eye drops following the 08:00 IOP measurement at the investigative site (the doctor's office).

IOP will be measured at 08:00, 12:00 and 16:00 (± 60 minutes). At these scheduled visits, BCVA and slit-lamp biomicroscopy will be performed just prior to the 08:00 IOP measurement. Ophthalmoscopy (fundus examination) will be performed after 16:00 IOP measurement.

Pharmacogenomics/Genomics:

Subjects who consent to the optional pharmacogenomics/genomics laboratory study will provide a blood sample for future testing. The purpose of this exploratory research is to identify possible genetic markers associated with the study medication(s) and/or ocular conditions.

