4.4. End of Study Definition

A subject is considered to have completed the study if he/she has completed all visits of the study including the last visit or the last scheduled procedure shown in the Schedule of Activities. The end of the study is defined as the date of the last visit of the last subject in the study.

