8.1.4. Visit 3 (Week 2, Day 15 ± 2)

- Update concomitant medications and procedures/therapies.
- A study staff member should query the subject regarding dosing compliance and ensure subject has sufficient study medication to complete dosing through Visit 4.
 - Subjects will be counseled on proper dosing procedures and dosing schedule if the subject’s compliance is not 100%. If a subject deviates from the prescribed dosage regimen, the specific dates of the missed doses should be recorded.
- Query the subject regarding AEs.

- As per the SoA ([Table 3](#)) and Procedures of Assessments ([Section 8.2](#)), perform the following procedures or assessments immediately before the 08:00 IOP measurement (all ophthalmic procedures to be performed in both eyes):
 - BCVA (prior to the 08:00 IOP measurement)
 - If more than 10 letters in BCVA were lost compared to the screening visit, then refraction should be performed again.
 - Biomicroscopy (prior to the 08:00 IOP measurement)
- Perform IOP measurement at 08:00 (± 60 min).
- Instill study medication/eye drop after the 08:00 IOP measurement in both eyes. A study staff should make sure the instillation is performed.
- Perform IOP measurement at 12:00 and 16:00 (± 60 min).
- If the subject provided written consent to provide a blood sample for a future pharmacogenomics/genomics laboratory research study, collect the sample at this visit or subsequent visit prior to exit from the study.
 - Note: If a blood sample cannot be collected at this visit, it may be collected at Visit 4 or unscheduled or early termination visit.
- Schedule the subject to return on Day 43 ± 3 for Visit 4 (Week 6).
- Remind the subject to continue dosing according to the written instructions.
- Inform the subjects they will be reminded of the morning and evening instillation of the study medication by phone call a few days before Visit 4.
- Remind the subjects that the morning dose of Visit 4 will be done at the clinic.
- Remind the subject to bring all used and unused study medication at Visit 4.

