7.7. Exposure to Study Medication

The duration of exposure to a study medication is measured by days on treatment as derived in [Section 4.1.3](#). For subjects in the Safety Population, the duration of exposure will be summarized using descriptive statistics, and frequency and percentage of subjects will be tabulated by duration category (1-14 days, 15-28 days, or > 28 days) for each actual treatment received.

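### When the last-dose date is missing, the fallback in SAP 4.1.2 can end treatment before the first dose or before a staff-checked clinic dose, closing the treatment-emergent window too early for a few subjects

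*SAP*

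**What the plan says.** SAP 4.1.2 defines treatment end as the date of the last dose and gives three fallbacks when that date is missing:

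- Completers: "The day before the Visit 4 (Week 6) will be considered the treatment end date for subjects who completed the study".
- Non-completers with an Exit Visit: "The day before the Exit Visit date will be used for subjects who prematurely discontinued from the study".
- Non-completers without an Exit Visit date: "then the day before the last available visit date will be considered the treatment end date".

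No branch is bounded below by the treatment start date or refers to doses taken in the clinic. None covers subjects who stop drug but stay in the study.

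The protocol places the first dose at 20:00 on the day of Visit 2 (Protocol 4.1 and 8.1.3). At Visit 3 the morning dose is given in the clinic after the 08:00 IOP reading: "A study staff should make sure the instillation is performed" (Protocol 8.1.4). Completion is defined by visits: "A subject is considered to have completed the study if he/she has completed all visits of the study" (Protocol 4.4). Protocol 7.1 encourages subjects who stop drug to attend the remaining visits.

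**The concern.** Treatment end feeds several safety derivations. It sets the treatment-emergent window, which runs to two days after treatment end (SAP 4.3.1), and only treatment-emergent AEs are tabulated. It also enters exposure (SAP 7.7), the compliance denominator (SAP 7.6) and the overlap test for concomitant medication (SAP 4.4.1).

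An end date that is too early removes AEs from the tables for subjects who may still have been dosing at home. This runs against the plan's approach to missing dates elsewhere: Protocol 9.3.5 asks for conservative imputation of event dates, and SAP Table 6 counts an AE with a wholly missing onset date as treatment-emergent. An end date that is too late overstates exposure. The safety objective is the comparison of BID with QD, so these tables matter even though they carry no formal test.

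**Working it through.** **Inputs.** Visit 2 is Day 1. Visit 3 is Day 13 to 17 and Visit 4 is Day 40 to 46 (Protocol Table 3). The first dose is taken to be on Day 1. The exposure categories are 1-14, 15-28 and >28 days (SAP 7.7). SAP 4.1.3 has no Day 0, so the day before Visit 2 is Study Day -1.

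**Assumption.** Exposure = end date - start date + 1. SAP 7.7 refers to SAP 4.1.3 for the derivation, but that section defines study day and gives no exposure formula.

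**Window.** Last treatment-emergent day = end date + 2 days.

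**1. Dosed subject lost after Visit 2**
- Imputed end: Visit 2 date - 1, which is Study Day -1 and precedes the start.
- Exposure: -1 + 1 = 0 days, in no category.
- Window closes at Visit 2 date - 1 + 2 = Visit 2 date + 1 = Day 2.
- The treatment period is inverted, so the overlap test for concomitant medication has no clear meaning.
- The compliance denominator would be 2 × (-1) = -2. This does not arise in practice: without a post-baseline IOP the subject is outside the FAS, on which SAP 7.6 is run.

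**2. Subject lost after Visit 3**
- Imputed end: Visit 3 - 1, one day before the clinic dose.
- Window closes at Visit 3 - 1 + 2 = Visit 3 + 1, whatever the visit day.

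| Visit 3 on | Imputed exposure | Exposure to the clinic dose | Category changes? |
|---|---|---|---|
| Day 13 | 12 | 13 | no |
| Day 14 | 13 | 14 | no |
| Day 15 | 14 | 15 | yes, 1-14 instead of 15-28 |
| Day 16 | 15 | 16 | no |
| Day 17 | 16 | 17 | no |

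With Visit 3 on Day 15 the window closes on Day 16. An AE on Day 20, reported by a subject still dosing at home, would not be tabulated.

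**3. Subject who stopped drug but completed all visits, last-dose date not captured**
- Illustration: drug stopped on Day 16, Visit 4 on Day 43. Imputed end is Day 42.
- Exposure is 42 days instead of 16, an overstatement of 26 days (>28 instead of 15-28).
- The window runs to Day 44 instead of Day 18.

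**4. Ordinary completer, Visit 4 on Day 43**
- Imputed end is Day 42, giving 42 days against 43 if a clinic dose was given on Day 43. Both are in >28.
- AE collection stops at the exit visit (Protocol 8.3.1), so no AE is affected.

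**The case against.** The rule applies only when the last-dose date is missing, and the protocol takes steps to prevent that. Dosing is queried at Visits 3 and 4 and dates of missed doses are recorded (Protocol 6.4). Early Termination procedures are due on the day drug is stopped or as soon as possible afterwards (Protocol 7.1). Exit forms are completed for all enrolled subjects (Protocol 10.1.8), and SAP 7.1 summarises discontinuation from drug separately from discontinuation from the study. Case 3 therefore needs a stop whose date was still not captured.

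Case 1 is narrow. It needs a known first dose taken at home, an unknown last dose, no later visit and no Exit Visit date. An unscheduled visit, or an exit-form date treated as the Exit Visit date, would avoid it. In Case 2, a subject who phones in an AE can also be asked about dosing.

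All of this stands as a limit on frequency. It does not make the rule right where it applies: an end before the start is a logical failure, and the early cut-off after Visit 3 occurs on every permitted visit day.

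A reader might infer that AEs disappear from the report. They do not: on-study AEs are recorded (SAP 4.3.1) and AEs are listed (SAP 9.1). What is lost is tabulation. A reader might also infer that exposure categories are generally wrong after Visit 3; the table shows a change only for Day 15.

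Protocol 6.2.2, which has dosing run through the morning before Visit 4, could be read as explaining the day-before rule for completers. It conflicts with Protocol Table 3 and 8.1.5, which place a clinic dose on the day of Visit 4. Visit 3 has no such conflict.

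**Conclusion.** The point holds as a fault in a stated derivation rule with limited reach. For dosed subjects lost after Visit 2 or Visit 3 whose last-dose date is missing, the imputed end is too early, and the treatment-emergent window closes on Day 2 or on the day after Visit 3. For early stoppers who completed the visits without a captured date, exposure is overstated, by 26 days in the illustration.

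The documents give no count of missing dates. The number is probably small and may be zero; Protocol 7.2 expects withdrawal to be uncommon. The 0-day figure rests on the assumed exposure formula, but the reversed order of start and end does not.

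Two larger conclusions are not supported. The primary IOP analysis (SAP 8.1.1) does not use treatment end, so the efficacy result is not at risk. The rule is the same in both arms, and nothing in the documents shows that missing dates would fall unequally between them or cluster where AEs are most serious, so a biased safety comparison cannot be claimed.

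**What to change.** Reword SAP 4.1.2 before unmasking:

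- **(a) Floor.** The imputed end date is never earlier than the treatment start date or the date of the last visit with a documented in-clinic dose. Case 1 then ends on Day 1 with 1 day of exposure (1-14). Case 2 with Visit 3 on Day 15 ends on Day 15 with 15 days.
- **(b) Drug stoppers.** For subjects recorded as having discontinued study drug, use the recorded drug discontinuation date, whether or not they completed the visits.
- **(c) Unknown last dose.** Only where no drug discontinuation is recorded and the last dose is unknown, class AEs from first dose to last contact as treatment-emergent. The floor alone would move the Case 2 window only from Day 16 to Day 17. Rule (c) must stay restricted: applied to everyone, it would count off-drug AEs for known early stoppers, which is the Case 3 problem again.

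State the exposure formula in SAP 7.7. Reconcile Protocol 6.2.2 with Protocol Table 3 and 8.1.5 on the last dose before the completer branch is reworded.

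The cost is SAP wording and a few lines of derivation code. The downside is that (c) may include a few off-drug AEs, which is the cautious direction for safety.
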